4.0 TREATMENT PLAN

4.1 Treatment Dosage and Administration

- 4.1.1 For the purpose of this study, the investigational products are avelumab, axitinib, and bavituximab. All investigational drugs will be administered on an outpatient basis.
- 4.1.2 Avelumab dosage form and packaging: Avelumab is a sterile, clear, and colorless solution intended for IV administration. Avelumab is formulated as a 20.0 mg/mL solution and will be supplied by Pfizer in single-use glass vials, stoppered with a rubber septum and sealed with an aluminum polypropylene flip-off seal. Avelumab will be dosed at the investigational site. For application in this trial, avelumab drug product must be diluted with 0.9% saline solution (sodium chloride injection).
- 4.1.3 Avelumab administration: Avelumab will be administered as a 1-hour IV infusion on Day 1 and Day 15 of each 28-day cycle. Avelumab may be administered up to 3 days before or after the scheduled Day 1 of each dose due to administrative reasons. Avelumab should be administered at least 30 minutes after the bavituximab infusion (on days when both are administered). In order to mitigate infusion-related reactions, a required premedication regimen of 25 to 50 mg IV or oral equivalent diphenhydramine and 650 mg IV or oral equivalent acetaminophen will be administered immediately prior to administration of avelumab for the first 4 infusions of avelumab. Premedication should be administered for subsequent avelumab doses based upon clinical judgment and presence/severity of prior infusion reactions. Sites should make every effort to target infusion timing to be as close to 1 hour as possible (no longer than 2 hours).

The dose amount required to prepare the avelumab infusion solution will be based on the patient's weight in kilograms (kg). All patients should be weighed within 7 days prior to dosing for every cycle. If the patient experienced either a weight loss or gain >10% compared to the weight used to calculate the prior dose, the amount of study drug required for preparation and administration for the current cycle must be recalculated using this most recent weight obtained. The maximum dose is 2000 mg for all adult patients. Avelumab dose reduction for toxicity management is not permitted, however next cycle administration may be omitted due to persisting toxicity.

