- 4.1.4 Axitinib dosage form and packaging: Axitinib will be supplied by Pfizer as 1 mg and 5 mg film-coated tablets for oral administration in light-resistant high-density polyethylene (HDPE) bottles with desiccant.
- 4.1.5 Axitinib administration: Axitinib will be provided in quantities appropriate for the study visit schedule. A qualified staff member will provide the study treatment via a unique container number. Axitinib will be dispensed every 4 weeks or as otherwise indicated.

Axitinib will be administered orally BID at approximately the same time in the morning and evening on a continuous dosing schedule. Axitinib tablets are to be taken approximately 12 hours apart and may be administered without regard to meals or avelumab and bavituximab administration. Tablets must not be crushed, split, or dissolved, and patients should be instructed to swallow the study medication whole without manipulation or chewing of the medication prior to swallowing.

Patients must be instructed that if they miss a dose or vomit any time after taking a dose, they must not "make it up" with an extra dose, but instead resume subsequent doses as prescribed. Any missed dose may be taken late, up to 3 hours, before the next scheduled dose of that day, otherwise, it should be skipped and dosing resumed with subsequent doses as prescribed. Patient must be instructed to record all doses (missed or vomited doses or extra doses) in a dosing diary supplied by the site.

- 4.1.6 Bavituximab dosage form and packaging: Bavituximab is supplied OncXerna as a sterile, preservative-free solution with 10 mM acetate at pH 5.0 and diluted with 0.9% saline (normal saline) to a final volume of 100 mL.
- 4.1.7 Bavituximab administration: Bavituximab will be administered weekly on Days 1, 8, 15 and 22 of the 28-day cycle.

Infusion preparation and administration are to be performed as follows:

1. Draw up the volume of a vial using a sterile syringe attached to an appropriate needle (a vented spike or other appropriate transfer device may be used). Fill treatment into a sterile glass bottle or plastic IV bag.
2. Using aseptic techniques, repeat procedure until the calculated volume has been put into the container. Bring the final volume to 100 mL using 0.9% Sodium Chloride Injection, USP.
3. Administer through a low protein binding 0.2-micrometer in-line filter (placed as proximal to the patient as practical).

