4.2.2 Axitinib dose reduction and re-escalation

Dosing interruption and/or dose reduction by 1, and if needed, 2 dose levels (one dose level decrease at a time) as indicated in Table 1 will be allowed depending on the type and severity of toxicity encountered. Patients who have undergone dose reduction may undergo dose re-escalation to prior dose levels in the absence of grade 2 or greater AEs for at least 28 days.

If patient develops decompensated cirrhosis (Child Pugh B), axitinib dosing should be reduced to the -1 dose level. Subsequent dosing can be increased or decreased according to the patient's tolerance. Patients must not have irreversible toxicities related to the axitinib to be eligible for dose re-escalation of axitinib after dose reduction.

Table 1. Axitinib dose levels.

Dose level	Dose
0	5 mg BID
-1	3 mg BID
-2	2 mg BID

Further dose reductions less than dose level -2 are not permitted.

4.2.3 Axitinib dose modifications, and avelumab and bavituximab infusion omissions for treatment-related toxicities.

Toxicities related to axitinib may primarily stem from the known on-target effects of inhibiting VEGFR including hypertension and proteinuria. In contrast, toxicities related to avelumab and bavituximab may be due to immune related AEs (irAEs). Management of specific irAEs should be consistent with American Society of Clinical Oncology (ASCO) Clinical Practice Guidelines (2018). For Grade 2 irAEs, avelumab and bavituximab should be permanently discontinued if AE does not resolve to at least Grade 1 within 12 weeks of last dose or corticosteroids cannot be reduced to ≤ 10 mg prednisone or equivalent per day within 12 weeks. Specific dose modifications and infusion omissions depend on the severity of toxicities as detailed in Table 2 and Table 3.

If any study drug is withheld or discontinued, the remaining study drugs can be continued as long as the patient is experiencing clinical benefit, as determined by the investigator per medical judgment.

Table 2. Dose modifications and infusion omissions for toxicities.

Toxicity	NCI CTCAE Grade	Axitinib	Avelumab	Bavituximab
Hypertension	1	Continue at same dose level.	Continue as per schedule.	Continue as per schedule.
	2	If not on maximal anti-hypertensive treatment, institute new or additional antihypertensive medication and continue at the same dose level. If on maximal anti-hypertensive treatment, reduce by 1 dose level.	Continue as per schedule.	Continue as per schedule.

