	3	For first and subsequent occurrence, withhold until BP is less than 150/100 mm Hg and adjust antihypertensive medication. Then, reduce by 1 dose level and resume treatment.	Continue as per schedule.	Continue as per schedule.

		
If on maximal anti-hypertensive treatment, reduce by 1 dose level.
 
If axitinib dosing is interrupted, patients receiving antihypertensive medications should be monitored closely for hypotension as BP usually decreases within 1-2 days after the last dose.
		
	4	
Repeat dose reduction by one lower dose level.
 
Permanent discontinuation if already on maximal anti-hypertensive treatment.
	Continue as per schedule.	Continue as per schedule.
Proteinuria	1	Continue at same dose level.	Continue as per schedule.	Continue as per schedule.
	2-3	
Continue at same dose level if proteinuria is <2gm/24 hours.
 
If proteinuria is >2gm/24 hours, withhold until proteinuria is <2 g/24 hours.
 
Time of repeat urine collection is at investigator discretion.
 
Then, resume at the same dose level or reduce by 1 dose level as per investigator judgment.
	Continue as per schedule.	Continue as per schedule.
irAEs (except for endocrinopathies)	1	Continue at same dose level.	Continue as per schedule.	Continue as per schedule.
	2	Continue at same dose level.	Withhold until Grade ≤1. If Grade 2 event does not resolve to Grade 1 after holding for at least 2 cycles (8 weeks), permanently discontinue.	Withhold until Grade ≤1. If Grade 2 event does not resolve to Grade 1 after holding for at least 2 cycles (8 weeks), permanently discontinue.
	3-4	Hold treatment until Grade ≤1 and restart at same dose level.	Permanently discontinue.	Permanently discontinue.
Immune related hypothyroidism	1	Continue at same dose level.	Continue as per schedule.	Continue as per schedule.
	2	Continue at same dose level.	May hold until patient is on thyroid hormone supplementation or symptoms resolve to baseline.	May hold until patient is on thyroid hormone supplementation or symptoms resolve to baseline.

	3-4	Hold treatment until Grade ≤ 1 and restart at same dose level.	Hold until symptoms resolve to baseline or until Grade ≤ 1 while on thyroid supplementation. Patient should be referred to Endocrine.	Hold until symptoms resolve to baseline or until Grade ≤ 1 while on thyroid supplementation. Patient should be referred to Endocrine.

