Immune related diabetes	1	Continue at same dose level.	Continue as per schedule.	Continue as per schedule.
	2	Continue at same dose level.	Considering holding until patient is stabilized (Grade ≤ 1) on replacement therapy. Insulin should be initiated as default treatment rather than oral therapies. Patient should be referred to Endocrine.	Considering holding until patient is stabilized (Grade ≤ 1) on replacement therapy. Insulin should be initiated as default treatment rather than oral therapies. Patient should be referred to Endocrine.
	3-4	Hold treatment until Grade ≤ 1 and restart at same dose level.	Hold until patient is stabilized (Grade ≤ 1) on replacement therapy. Insulin should be initiated as default treatment rather than oral therapies. Patient should be referred to Endocrine.	Hold until patient is stabilized (Grade ≤ 1) on replacement therapy. Insulin should be initiated as default treatment rather than oral therapies. Patient should be referred to Endocrine.
Immune related colitis/diarrhea	1	Continue at same dose level.	Consider holding until symptoms resolve to baseline or until Grade ≤ 1 . Consider antidiarrheals if other causes are excluded.	Consider holding until symptoms resolve to baseline or until Grade ≤ 1 . Consider antidiarrheals if other causes are excluded.
	2	Continue at same dose level.	Hold until symptoms resolve to baseline or until Grade ≤ 1 . Steroids may be considered if indicated on an individual basis.	Hold until symptoms resolve to baseline or until Grade ≤ 1 . Steroids may be considered if indicated on an individual basis.
	3	Hold treatment until Grade ≤ 1 and restart at same dose level.	Hold until symptoms resolve to baseline or until Grade ≤ 1 . Administer steroids at 1-2 mg/kg/d prednisone or equivalent with taper over 4 weeks. Patient should be referred to Gastroenterology. Consider colonoscopy.	Hold until symptoms resolve to baseline or until Grade ≤ 1 . Administer steroids at 1-2 mg/kg/d prednisone or equivalent with taper over 4 weeks. Patient should be referred to Gastroenterology. Consider colonoscopy.
	4	Permanently discontinue.	Permanently discontinue.	Permanently discontinue.
Immune related pneumonitis	1	Continue at same dose level.	Hold if there is progression with repeat CT chest at 3-4 weeks and treat as Grade 2.	Hold if there is progression with repeat CT chest at 3-4 weeks and treat as Grade 2.

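### For a non-endocrine Grade 2 immune-related event, Section 4.2.3 and its own Table 2 give different permanent-stop limits for avelumab and bavituximab (12 weeks from last dose against at least 8 weeks of holding)

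*Combined protocol and SAP*

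**What the plan says.** Three parts of Section 4.2.3 bear on a Grade 2 irAE.

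- **Text before Table 2.** "avelumab and bavituximab should be permanently discontinued if AE does not resolve to at least Grade 1 within 12 weeks of last dose". A second trigger applies if "corticosteroids cannot be reduced to ≤ 10 mg prednisone or equivalent per day within 12 weeks". The paragraph then sends the reader to the tables: "Specific dose modifications and infusion omissions depend on the severity of toxicities as detailed in Table 2 and Table 3".
- **Table 2, general irAE row (endocrinopathies excepted), Grade 2.** Axitinib continues unchanged. Avelumab and bavituximab are withheld until the event is Grade 1 or lower, and the same sentence then appears in both columns: "If Grade 2 event does not resolve to Grade 1 after holding for at least 2 cycles (8 weeks), permanently discontinue".
- **Table 2, organ-specific Grade 2 rows.** Colitis/diarrhea and hepatitis read: "Hold until symptoms resolve to baseline or until Grade ≤ 1 . Steroids may be considered if indicated on an individual basis". The pneumonitis row also holds until resolution, prescribes steroids, and moves to Grade 3 handling if there is no clinical improvement. None of the three states a limit in weeks.

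Section 4.2.3 also provides that "If any study drug is withheld or discontinued, the remaining study drugs can be continued as long as the patient is experiencing clinical benefit". A permanent stop of the two antibodies therefore need not end axitinib.

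**The concern.** Two permanent-stop limits are stated for the same event, the same grade and the same two drugs, a few lines apart. They differ in length (12 against 8 weeks) and in when the clock starts (last dose against the hold). The table's limit is worded as a minimum with no maximum. The text's pointer to the tables is a cross-reference, not an order of precedence. If the table were meant to govern, the 12-week resolution limit would have no effect in the general row.

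At stake is whether a patient permanently loses two of the three study drugs. This is first a matter of patient safety and consistent conduct. It also affects exposure, since Section 10.3 plans a summary of cycles and doses administered. The trial has two centers and at most 29 evaluable patients, so handling should not depend on which sentence an investigator happens to read.

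**Working it through.** **Inputs**
- Text limit: 12 weeks from last dose (Section 4.2.3).
- Table limit: 2 cycles of holding, glossed as 8 weeks (Table 2, general irAE row, Grade 2).
- Avelumab interval, 2 weeks: "Avelumab will be administered as a 1-hour IV infusion on Day 1 and Day 15 of each 28-day cycle" (Section 4.1.3).
- Bavituximab interval, 1 week: "Bavituximab will be administered weekly on Days 1, 8, 15 and 22 of the 28-day cycle" (Section 4.1.7).

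**Step 1: the table's own figure.** 2 cycles × 28 days ÷ 7 = 8 weeks. The table agrees with itself, so the discrepancy is not a slip in converting cycles to weeks.

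**Step 2: both limits on one clock.** The documents do not define when a hold begins, so both readings are shown. Each drug is counted from its own last dose, and infusions are assumed to have been on schedule before the hold.

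Table limit in weeks from last dose = 8 + offset. The offset is 0 if the hold is counted from the last dose, or one dosing interval if it is counted from the first omitted infusion. Window of disagreement = 12 − table limit.

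| Drug | Hold counted from | Table limit | Text limit | Window |
|---|---|---|---|---|
| Avelumab | last dose | 8 + 0 = week 8 | week 12 | 4 weeks |
| Avelumab | first omitted infusion | 8 + 2 = week 10 | week 12 | 2 weeks |
| Bavituximab | last dose | 8 + 0 = week 8 | week 12 | 4 weeks |
| Bavituximab | first omitted infusion | 8 + 1 = week 9 | week 12 | 3 weeks |

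**Step 3: when the outcome differs.** On the plain reading, the table orders a stop once 8 weeks of holding pass without resolution.
- Resolved before the table limit: neither resolution limit triggers a stop.
- Resolved after the table limit but by week 12: stopped under Table 2, not stopped under the text.
- Unresolved at week 12: stopped under both.

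An event that resolves at week 11 falls in the middle group for both drugs on either count of the hold.

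**Step 4: steroids.** The text's steroid trigger does not appear in the general Table 2 row. The text also gives no starting point for the 12 weeks in that trigger.

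**Step 5: organ-specific rows.** With no limit in weeks in the colitis, pneumonitis and hepatitis Grade 2 rows, two readings are open. If the specific row replaces the general one, only the 12-week text sets a limit in weeks for those events and the 8-against-12 conflict does not reach them. If the general row also applies, it does. The documents do not say which.

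**The case against.** The best reconciling argument is that *at least* makes 8 weeks a minimum hold, with the text's 12 weeks as the outer limit. The two rules would then largely fit together. This reading is possible, but no section states it. The row gives no outer limit of its own, and the reading leaves undefined what happens between the two points. It calls for the same edit.

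A reader might infer that a site obeying one sentence must breach the other. The documents do not support that. The text requires a stop if the event is unresolved at 12 weeks; it neither requires resumption before then nor forbids stopping earlier. Section 5.4 lets the physician stop treatment for toxicity or in the patient's interest. Stopping at 8 weeks under Table 2 therefore breaches nothing in the text. Only resuming after the table limit departs from a stated rule, and permission to do so is implied by the text, not given outright.

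A reader might also infer that the steroid rules contradict each other. They do not. The row is silent on steroids, and the text's condition can apply alongside it. The defect is an omission that someone working from the table alone would miss.

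Finally, registration and toxicity review run through one disease-oriented team (Sections 4.4 and 11.4), which makes divergent handling by the two centers less likely. That is fair, but the team would still have to choose between two written limits.

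**Conclusion.** The point holds in a limited form. Section 4.2.3 states two different permanent-stop limits for avelumab and bavituximab after a non-endocrine Grade 2 irAE, without precedence. On the plain reading of the table, they disagree over a window of 2 to 4 weeks for avelumab and 3 to 4 weeks for bavituximab, depending on when the hold is taken to start. The missing steroid condition and the unclear standing of the three organ-specific rows are related gaps.

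It would be tempting to conclude that response rate, duration of response or progression-free survival will be distorted. The documents do not support this for the triplet: they give no frequency of Grade 2 irAEs that resolve inside the window, so no effect can be calculated. The sample-size and error-rate calculations in Section 10.2 do not use this rule and are unaffected. The case for correction rests on patient safety and uniform exposure. No view is taken here on which limit is clinically right.

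**What to change.** In the next amendment, reconcile the Section 4.2.3 text with the general irAE row of Table 2 so that both state:

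- one time limit, with *at least* replaced by a definite limit;
- one starting point for the clock, with the start of a hold defined if that is the one used;
- the same steroid condition, with its own starting point.

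State also whether the general row's limit applies to the Grade 2 colitis, pneumonitis and hepatitis rows, or whether those rows stand alone. The clinical leads choose the rule. The cost is a wording change, with no additional patients or procedures and no change to the statistical design.

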4.2.1 Safety Lead-in and Dose-limiting Toxicities

A safety and tolerability assessment will be performed for patients treated with axitinib, bavituximab, and avelumab after the first 6 patients evaluable for dose-limiting toxicities have completed 1 cycle (ie, Cycle 1 Day 28). Patients will be considered evaluable for dose-limiting toxicities assessment if they have completed all scheduled study visits during the first cycle and have received 2 (100%) of the 2 planned doses of avelumab and at least 3 (75%) of the 4 planned doses of bavituximab in Cycle 1.

Dose-limiting toxicities are defined as any Grade 3 or greater AE that occurs during the first cycle (28 days) and are considered to be related (possible, probable, or definite) to study drug, specifying attribution to axitinib, avelumab, bavituximab, or all drugs. Intolerable Grade 2 gastrointestinal toxicities (such as persistent nausea/vomiting or diarrhea) will also be considered dose-limiting toxicities if they are considered to be related to any study drug. See Tables 2 and 3 below and Section 7.0 for AEs associated with axitinib, avelumab, or bavituximab.

Enrollment of additional patients after the first 6 potentially evaluable patients for dose limiting toxicities will be suspended until after assessment of the safety lead-in phase by the UTSW Simmons Cancer Center Gastrointestinal Disease-Oriented Teams (GI DOT) is complete.

- If ≤ 1 dose-limiting toxicity occurs, trial enrollment will proceed without any modifications.
- If ≥ 2 dose-limiting toxicities occurs, all treatment-related AEs will be reviewed by the GI DOT for consideration of modification or termination of the study. Modifications may include reducing the starting dose of axitinib by one dose level to 3 mg BID for all subsequent patients enrolled and not permitting dose re-escalation above dose level 0.

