	3-4	Hold until symptoms resolve to baseline or until Grade ≤ 1 . Then, reduce by 1 dose level.
Hematologic abnormalities	1-3	Continue at same dose level.

	4	Hold until symptoms resolve to baseline or until Grade ≤1. Restart axitinib dose reduced by 1 dose level. Note: Grade 4 lymphopenia not associated with clinical events, (e.g, opportunistic infection) may continue on with axitinib.
Stevens-Johnson syndrome	3-4	Permanently discontinue.
Other non-hematologic toxicities and laboratory abnormalities	1-2	Continue at same dose level.
	3	Hold until symptoms resolve to baseline or until Grade ≤2. For toxicities controlled with symptomatic medications or asymptomatic laboratory abnormalities, continue at the same dose level or reduce by 1 dose level as per investigator judgment. For all other toxicities, reduce by 1 dose level.
	4	Hold until symptoms resolve to baseline or until Grade ≤2. Then, reduce by 1 dose level as per investigator judgment. Permanently discontinue axitinib for Grade 4 toxicities that meet any of the following conditions: 1) recurrent 2) life-threatening 3) reversible posterior leukoencephalopathy syndrome 4) arterial thrombosis/ischemia

4.2.4 Infusion related reactions.

Because avelumab and bavituximab are administered as infusions, infusion reactions are possible and may include symptoms such as fever, chills, shortness of breath, headache, and rigors. Infusion modifications depend on the severity of reactions as detailed in Table 4 below.

Table 4. Infusion-related reactions caused by avelumab or bavituximab.

NCI CTCAE Grade	Infusion modifications
1	Decrease the avelumab and/or bavituximab infusion rate by 50%.
2	Temporarily discontinue avelumab and/or bavituximab infusion. Resume infusion at 50% of previous rate once infusion-related reaction has resolved or decreased to at least Grade 1 in severity, and monitor closely for any worsening.
3-4	Stop the infusion immediately and disconnect infusion tubing from the patient. Patients may not receive further treatment.

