4.7 Removal of Subjects from Protocol Therapy

Subjects will be removed from therapy when any of the criteria listed in Section 5.4 apply. Notify the Principal Investigator and document the reason for treatment discontinuation and the date of discontinuation. The subject should be followed-up per protocol.

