5.4 Removal of Subjects from Study

Subjects can be taken off the study treatment and/or study at any time at their own request, or they may be withdrawn at the discretion of the investigator for safety, behavioral or administrative reasons. The reason(s) for discontinuation will be documented and may include:

- 1) Subject voluntarily withdraws from treatment (follow-up permitted).
- 2) Subject withdraws consent (termination of treatment and follow-up).
- 3) Subject is unable to comply with protocol requirements.
- 4) Subject demonstrates clinical or radiographic evidence of disease progression based on Investigator assessment (note, continued treatment with study drug/treatment including treatment beyond RECIST 1.1 progression is deemed appropriate at the discretion of the investigator, but patients must discontinue trial treatment if progression is confirmed based on iRECIST).
- 5) Subject experiences toxicity that makes continuation in the protocol unsafe.
- 6) Treating physician judges that continuation on the study would not be in the subject's best interest.
- 7) Subject becomes pregnant (pregnancy to be reported along same timelines as a serious adverse event).
- 8) Development of second malignancy (except for basal cell carcinoma or squamous cell carcinoma of the skin) that requires treatment, which would interfere with this study.
- 9) Lost to follow-up. If a research subject cannot be located to document survival after a period of 6 months, the subject may be considered "lost to follow-up".

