7.1.2 Special Warnings and Precautions for Use

Aneurysms and artery dissections

VEGF pathway inhibitors may promote the formation of aneurysms and/or artery dissections. Before initiating axitinib, this risk should be carefully considered in patients with risk factors such as hypertension or history of aneurysm.

Elevation of Hemoglobin or Hematocrit

Increases in hemoglobin or hematocrit, reflective of increases in red blood cell mass, may occur during treatment with axitinib. An increase in red blood cell mass may increase the risk of thromboembolic events.

Hemoglobin or hematocrit should be monitored before initiation of, and periodically throughout, treatment with axitinib. If hemoglobin or hematocrit becomes elevated above the normal level, patients should be treated according to standard medical practice to decrease hemoglobin or hematocrit to an acceptable level.

Gastrointestinal Perforation and Fistula Formation

In pooled clinical studies with axitinib for the treatment of patients with renal cell carcinoma, gastrointestinal perforation and fistula were reported in 13/672 patients (2%) receiving axitinib. Monitor for symptoms of gastrointestinal perforation periodically throughout treatment with axitinib.

Wound Healing Complications

In the Phase 3 study A4061032 with axitinib for the treatment of patients with renal cell carcinoma, all-causality adverse events suggestive of wound healing complications were reported in 4/359 patients (1%). Treatment with axitinib should be stopped at least 24 hours prior to scheduled surgery. The decision to resume axitinib therapy after surgery should be based on clinical judgment of adequate wound healing.

Reversible Posterior Leukoencephalopathy Syndrome

In pooled clinical studies with axitinib for the treatment of patients with renal cell carcinoma, reversible posterior leukoencephalopathy syndrome was reported in 2/672 patients (<1%) receiving axitinib. In patients with signs/symptoms of reversible posterior leukoencephalopathy syndrome, axitinib should be permanently discontinued.

Heart failure events

In a controlled clinical study with axitinib for the treatment of patients with Renal Cell Carcinoma (RCC), heart failure events were reported in 1.7% of patients receiving axitinib. Grade 3/4 and 5 cardiac failure events were observed in 0.6% and 0.6% of patients receiving axitinib, respectively. Monitor for signs or symptoms of cardiac failure periodically throughout treatment with axitinib.

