7.4.1 Definitions

An adverse event is defined as any untoward or unfavorable medical occurrence in a human research study participant, including any abnormal sign (for example, abnormal physical exam, imaging finding or clinically significant laboratory finding), symptom, clinical event, or disease, temporally associated with the subject's participation in the research, whether or not it is considered related to the subject's participation in the research.

Adverse events encompass clinical, physical, and psychological harms. Adverse events occur most commonly in the context of biomedical research, although on occasion, they can occur in the context of social and behavioral research. Adverse events may be expected or unexpected.

Severity

Adverse events will be graded by a numerical score according to the defined NCI Common Terminology Criteria for Adverse Events (NCI CTCAE) Version 5.0. Adverse events not specifically defined in the NCI CTCAE will be scored on the Adverse Event log according to the general guidelines provided by the NCI CTCAE and as outlined below.

- Grade 1: Mild
- Grade 2: Moderate
- Grade 3: Severe or medically significant but not immediately life threatening
- Grade 4: Life threatening consequences
- Grade 5: Death related to the adverse event

Serious Adverse Events

OHRP and UTSW HRPP define serious adverse events as those events, occurring at any dose, which meets any of the following criteria:

- results in death;
- is life-threatening (places the subject at immediate risk of death from the event as it occurred);
- results in inpatient hospitalization^{1,2} or prolongation of existing hospitalization;
- results in a persistent or significant disability/incapacity;

- results in a congenital anomaly/birth defect; or
- based upon appropriate medical judgment, may jeopardize the subject's health, and may require medical or surgical intervention to prevent one of the other outcomes listed in this definition.

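### Section 7.1.2 stops axitinib permanently for symptomatic reversible posterior leukoencephalopathy syndrome with no grade limit, but Table 3 names the syndrome only at Grade 4, so lower grades get a different literal instruction

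*Combined protocol and SAP*

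**What the plan says.** Two places in the protocol attach an action to RPLS.

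- **Section 7.1.2 (axitinib warnings):** "In patients with signs/symptoms of reversible posterior leukoencephalopathy syndrome, axitinib should be permanently discontinued". The trigger is signs or symptoms. No grade is mentioned.
- **Section 4.2.3, Table 3, row for other non-hematologic toxicities and laboratory abnormalities, Grade 4 cell:** "Permanently discontinue axitinib for Grade 4 toxicities that meet any of the following conditions". RPLS is the third of four conditions. The others are recurrence, a life-threatening event, and arterial thrombosis or ischemia.

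Neither Table 2 nor Table 3 has a row for RPLS. Section 7.1.4 lists the syndrome, under its alternative name, as a suspected axitinib reaction, but gives no grade or action.

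On how the texts relate, Section 4.2.3 says "Specific dose modifications and infusion omissions depend on the severity of toxicities as detailed in Table 2 and Table 3". Section 4.2.1 adds "See Tables 2 and 3 below and Section 7.0 for AEs associated with axitinib, avelumab, or bavituximab". Neither sentence says which text prevails where they differ.

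**The concern.** Staff who grade an event and look up the action will go to Table 3. For symptomatic RPLS below Grade 4, the table does not lead them to the action that Section 7.1.2 gives. A site applying the table literally would continue or restart axitinib in a patient for whom the protocol's own warning says to stop it for good. Section 11.5 expects the study to be run as written outside emergencies, so two different instructions for one serious neurological event should be reconciled. What is at stake is patient safety and consistent handling across the two sites, not the statistical analysis.

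**Working it through.** The plan gives no figure to reproduce here. The check is a comparison of texts.

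**Is RPLS within Table 3?** Table 3 covers drug-related events that may be associated with axitinib and are not considered immune-related. Section 7.1.4 lists the syndrome as a suspected axitinib reaction, so a case attributed to axitinib is in scope. With no row of its own, it can only enter through the catch-all row.

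**Can a symptomatic case be below Grade 4?** The general scale in Section 7.4.1 runs from mild through moderate to severe but not immediately life-threatening before it reaches "Grade 4: Life threatening consequences". Nothing in the documents fixes RPLS at Grade 4.

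**Actions for a symptomatic case, side by side:**

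| Grade | Table 3, read literally | Section 7.1.2 | Agree? |
|---|---|---|---|
| 1-2 | Continue axitinib, same dose | Stop permanently | No |
| 3 | Hold until baseline or Grade 2 or lower, then reduce one level; same dose possible only if controlled with symptomatic medication | Stop permanently | No |
| 4 | Stop permanently | Stop permanently | Yes |

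The default after a Grade 3 hold is "For all other toxicities, reduce by 1 dose level". The same-dose option has two routes. One is an asymptomatic laboratory abnormality, which cannot apply to a symptomatic patient. The other is control with symptomatic medication, and the documents do not say whether RPLS could meet it.

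**Does the table stop axitinib below Grade 4 for other events?** Yes, explicitly: Grade 1 CNS bleeding, Grade 2 pulmonary or gastrointestinal bleeding (with exceptions), Grade 3 bleeding and Grade 3 Stevens-Johnson syndrome. RPLS has no comparable entry.

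**Is the Grade 4 restriction likely to be deliberate?** Probably not. If Grade 4 means life-threatening, the second condition already captures every Grade 4 case, and naming RPLS adds nothing. The same is true of the other listed conditions. The redundancy therefore points to loose drafting of the whole cell and does not prove what was intended for RPLS.

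**How common is the event?** Section 7.1.2 reports 2/672 = 0.30% in pooled renal cell carcinoma studies of axitinib, at any grade.

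**The case against.** The strongest reply is that the texts can be reconciled. Section 7.1.2 names the syndrome. Below Grade 4, Table 3 reaches it only through a residual row, and a named instruction ordinarily prevails over a residual one. Wherever the protocol attaches an action to RPLS by name, that action is permanent discontinuation. This is a sensible reading and probably the one most investigators would adopt, but the protocol does not state it. Section 4.2.3 points the other way by assigning severity-based modifications to the tables.

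A second reply treats Section 7.1.2 as a general warnings summary never meant to match the table grade by grade. Bleeding illustrates this: the warning speaks of temporary interruption where Table 3 often requires permanent discontinuation. That may explain how the mismatch arose, but it leaves the difference below Grade 4 in place.

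A third reply is that the investigator can always stop. Section 4.7 says "Subjects will be removed from therapy when any of the criteria listed in Section 5.4 apply", and those criteria include "Subject experiences toxicity that makes continuation in the protocol unsafe" (criterion 5) and the treating physician's view of the subject's best interest (criterion 6). Nothing in Table 3 bars stopping. This stands and limits the harm, but both criteria depend on judgment, whereas Section 7.1.2 gives a direct instruction.

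Two stronger readings are tempting and are not supported:

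- **That the protocol directs rechallenge after RPLS.** No text says so by name. That result needs a literal use of the residual row with Section 7.1.2 set aside.
- **That the risk in this trial can be bounded.** Applying 2/672 to 29 patients gives 1 - (1 - 2/672)^29 = 8.3% for at least one case, which a reader might take as a ceiling. It is not one. The 29 counts evaluable patients, and Sections 10.1 and 10.2 replace some patients, so more may be treated. The rate comes from renal cell carcinoma, not from this triplet in hepatocellular carcinoma. The share of cases that are symptomatic and below Grade 4 is not given.

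**Conclusion.** The inconsistency is real and minor. For symptomatic RPLS at Grades 1 to 3, Table 3 read literally and Section 7.1.2 give different axitinib instructions, and no stated rule of precedence settles which applies. At Grade 4 they agree. The point is confined to symptomatic cases, because the Section 7.1.2 trigger does not clearly cover an asymptomatic imaging finding.

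The conclusion assumes that a site might use the catch-all row as written. A site that reads both texts would probably stop axitinib. The event is rare in the experience the protocol cites, and no probability can be given for the conflict occurring here. The objective response rate, sample size and error rates are unaffected.

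**What to change.** Delete RPLS from the Grade 4 condition list in Table 3 and add a separate row: signs or symptoms of reversible posterior leukoencephalopathy syndrome, any grade, permanently discontinue axitinib. This brings the table into line with Section 7.1.2. If a grade limit is actually intended, state it in Section 7.1.2 instead. The cost is one added row and one deleted list item, with no change to the design or analysis.
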